7.3 Blinding

This is an open-label study. Blinding procedures are not applicable.

7.4 Dosage Modification

Not Applicable

7.5 Preparation/Handling/Storage/Accountability

The investigational product should be stored in a secure area according to local regulations. It is the responsibility of the investigator to ensure that investigational product is only dispensed to study Participants. The investigational product must be dispensed only from official study sites by authorized personnel according to local regulations.

The product storage manager should ensure that the study treatment is stored in accordance with the environmental conditions (temperature, light, and humidity) as determined by BMS. If concerns regarding the quality or appearance of the study treatment arise, the study treatment should not be dispensed and contact BMS immediately.

Study treatment not supplied by BMS will be stored in accordance with the package insert.

Investigational product documentation (whether supplied by BMS or not) must be maintained that includes all processes required to ensure drug is accurately administered. This includes documentation of drug storage, administration and, as applicable, storage temperatures, reconstitution, and use of required processes (eg, required diluents, administration sets).

For study drugs not provided by BMS (enoxaparin and UFH) and obtained commercially by the site, storage should in accordance with the product label.

Compounding instructions for BMS-986177 will be provided separately to the site.

- Further guidance and information for final disposition of unused study treatment are provided in [Appendix 2](#).

7.5.1 Retained Samples for Bioavailability / Bioequivalence

Not Applicable

7.6 Treatment Compliance

Study drug will be administered in the clinical facility. After administration of BMS-986177 an examination of the oral cavity is required to verify that a participant has swallowed the solution. The participant should drink the entire aliquot of water given to swallow the solution.

Clinical Protocol
BMS-986177

CV010010
FXIa

UFH and Enoxaparin will be administered by the healthcare staff at the clinical facility according to protocol and standard of care.

7.7 Concomitant Therapy

7.7.1 Prohibited and/or Restricted Treatments

Prohibited and/or restricted medications taken prior to study drug administration in the study are described below. Medications taken within 4 weeks prior to study drug administration must be recorded on the CRF.

- 1) Use of any agent, including but not limited to anti-platelet agents (except aspirin), anticoagulants (except heparin for routine hemodialysis use), fish oil capsules, and ginkgo that is known to increase the potential for bleeding within 2 weeks prior to study drug administration. Use of non-steroidal anti-inflammatory compounds (NSAIDs) or aspirin within 1 week prior to study drug administration.
- 2) Exposure to any investigational drug or placebo within 4 weeks of study drug administration.
- 3) Use of acid controllers within two days of BMS-986177 study drug administration except those medications cleared by the BMS medical monitor. The use of acid controllers after BMS-986177 administration and after hemodialysis is allowed. The use of acid controllers is also allowed when enoxaparin or UFH are administered.
 - a) Sodium bicarbonate is allowed during the study.
- 4) Use of strong and moderate CYP3A inhibitors within 1 week of enrollment including the following: the antifungals and antibiotics ketoconazole, fluconazole, itraconazole, miconazole, clotrimazole, erythromycin and clarithromycin; the calcium channel blockers diltiazem and verapamil; the HIV anti-virals delaviridine, indinavir, nelfinavir, ritonavir, and saquinavir; and the serotonin reuptake inhibitor fluoxetine. Use of CYP3A inducers such as carbamazepine, dexamethasone, phenobarbital, phenytoin, rifampin, St John's Wort within 4 weeks of enrollment. Topical antifungal use is allowed.

Study patients may receive treatment with medications necessary for maintaining the clinical status of their condition as described in Inclusion Criteria.

Any concomitant therapies must be recorded on the CRF.

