2. SCHEDULE OF ACTIVITIES

Table 2.-1: Procedural Outline Screening		
Procedure	Screening Visit (up to 28 days prior to First Dose)^a	Notes
Eligibility Assessments		
Informed Consent	x	A participant is considered enrolled only when a protocol specific informed consent is signed.
Inclusion/Exclusion Criteria	x	
Medical History	x	Include any toxicities or allergy related to previous treatments.
Concomitant Medications	x	
Safety Assessments		
Physical Examination (PE)	x	If the screening PE is performed within 24 hours prior to dosing on Day 1 then a single exam may count as both the screening and pre-dose evaluation.
Physical Measurements	x	Includes height, weight, and BMI.
Vital Signs	x	Includes body temperature, respiratory rate, and seated blood pressure and heart rate. Blood pressure and heart rate should be measured after the participant has been resting quietly for at least 5 minutes.
Electrocardiogram (ECGs)	x	ECGs should be recorded after the participant has been supine for at least 5 minutes.
Laboratory Tests		
Drug Screen (urine or saliva)	x	
Alcohol Screen	x	Breathalyzer
Clinical Labs	x	Chemistry, CBC, Coagulation and urine dipstick for blood (if participant is able to produce urine).
Serology	x	HIV
Pregnancy test	x	WOCBP only. See Section 9.4.4 .
Stool sample for occult blood	x	Subjects may bring sample to the unit on or prior to D1.
Adverse Event Reporting		
Monitor for Serious Adverse Events	x	All SAEs must be collected from the date of participant's written consent until 30 days post discontinuation of dosing or participant's participation in the study if the last scheduled visit occurs at a later time.

^a Screening and Day -1 to -3 activities can be combined if performed on the same day

--

Clinical Protocol
BMS-986177

CV010010
FXIa

Table 2.-2: Procedural Outline Treatment

Procedure	D -1 to -3	D 1	D5	D8	D12	D13 to D15 /Study Discharge ^a	Notes
Safety Assessments							
Physical Examination (PE)	x						
Targeted PE		x	x	x	x	x	Targeted physical based on subject complaint.
Concomitant Medications	x	x	x	x	x	x	
Physical Measurements	x	x	x	x	x		Weight only. Collect prior to Day 1 visit and collect pre and post dialysis (SoC can be used).
Vital Signs	x	x	x	x	x	x	Includes body temperature, respiratory rate, seated blood pressure (BP), and heart rate (HR) on Day -1 to -3 and for those that discontinue prematurely. BP and HR (pre-dose & 3h post HD for all treatments on Days 1, 5, 8, and 12, at 24h post-dose only when BMS-986177 is administered).

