8. DISCONTINUATION CRITERIA

8.1 Discontinuation from Study Treatment

Participants MUST discontinue investigational product (and non-investigational product at the discretion of the investigator) for any of the following reasons:

- Participant's request to stop study treatment. Participants who request to discontinue study treatment will remain in the study and must continue to be followed for protocol specified follow-up procedures. The only exception to this is when a participant specifically withdraws consent for any further contact with him/her or persons previously authorized by participant to provide this information
- Any clinical adverse event (AE), laboratory abnormality or intercurrent illness which, in the opinion of the investigator, indicates that continued participation in the study is not in the best interest of the participant
- Termination of the study by Bristol-Myers Squibb (BMS)
- Loss of ability to freely provide consent through imprisonment or involuntarily incarceration for treatment of either a psychiatric or physical (eg, infectious disease) illness
- Pregnancy
- Overt bleeding producing a Hb decrease ≥ 2 g/dL in 24 hours
- Need for blood transfusion
- Overt bleeding which is retroperitoneal, intracranial, intra-spinal, intraocular, or intraarticular
- Any overt bleeding deemed by the investigator to necessitate discontinuation of trial medication
- Medical or surgical treatment for bleeding beyond the application of pressure or cold compress
- Need for surgery during the study period
- Need for treatment with an anticoagulant or antiplatelet agent during the study period, with the exception of heparin and enoxaparin use during HD
- Need for treatment with a strong CYP3A4 inhibitor or any CYP3A4 inducers
- Inability to continue on the hemodialysis treatment for the duration of the study
- Inability to comply with the protocol
- Occurrence in one of the BMS-986177 treatment arm or in the enoxaparin treatment arm of 5 or more patients with events of complete clotting of HD circuit causing premature interruption of the HD procedure. This will result in a discontinuation of that treatment arm. The randomized sequence for the following patients will not be changed, and the discontinued treatment arm will be replaced by standard of care (UFH) in the treatment sequence.

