## 6.3 Populations for Analyses

- All Enrolled Patients, defined as all patients who signed ICF;
- All Randomized Patients, defined as patients who were randomized to a sequence of treatments including the patients who replace the discontinuing randomized patients;
- Safety Population, defined as all randomized patients who took at least 1 dose of study treatment;
- Pharmacodynamic Population, defined as a subset of the Safety Population and includes all patients who received at least 1 dose of study treatment and had any available PD data;
- Biomarker Population, defined as a subset of the Safety Population and includes all patients who received at least 1 dose of study treatment and had any available post dose biomarker data;
- Pharmacokinetic Population, defined as all patients who received BMS-986177 from whom PK parameter data were obtained before and after HD.

- Evaluable PK Population, defined as a subset of the PK Population and includes all patients who had adequate PK profiles.

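### The CYP3A windows are counted from consent rather than from dosing, and the on-study stopping rule omits moderate inhibitors, so a moderate inhibitor can be taken around some BMS-986177 doses without breaking a stated rule

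*Protocol*

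**What the plan says.** **Pre-dose restriction.** Protocol Section 7.7.1 opens with a scope sentence: "Prohibited and/or restricted medications taken prior to study drug administration in the study are described below". Item 4 then restricts "Use of strong and moderate CYP3A inhibitors within 1 week of enrollment", followed by a list that does not mark which drugs are strong and which are moderate. The inducer list ends "phenobarbital, phenytoin, rifampin, St John's Wort within 4 weeks of enrollment". The other items use a different clock. Item 2, for example, reads "Exposure to any investigational drug or placebo within 4 weeks of study drug administration"; item 1 also counts from study drug administration, and item 3 (acid controllers) counts from the BMS-986177 dose itself.

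**Meaning of enrollment.** Protocol Table 2.-1 states: "A participant is considered enrolled only when a protocol specific informed consent is signed". SAP Section 6.3 agrees: "All Enrolled Patients, defined as all patients who signed ICF". Table 2.-1 heads its column "Screening Visit (up to 28 days prior to First Dose").

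**On-study rule.** The list of mandatory discontinuation reasons in Protocol Section 8.1 includes "Need for treatment with a strong CYP3A4 inhibitor or any CYP3A4 inducers". Moderate inhibitors do not appear there.

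**Analysis.** SAP Section 7.7 summarizes PK parameters by treatment. The patient-level exclusion reasons named in SAP Section 7.10.2 are missed doses, diarrhea and vomiting. Interacting medication is not named.

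**The concern.** Item 4 is the only item in its list tied to consent, and consent can precede the first BMS-986177 dose by weeks. A restriction meant to protect exposure around a dose should be in force around that dose, and here it may have lapsed. After first dosing the only explicit CYP3A rule is the one in Section 8.1, and it covers fewer drug classes than item 4. Because item 4 does not separate strong from moderate inhibitors, a site cannot tell from the protocol which of the listed drugs would trigger Section 8.1.

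Cmax, AUC and dialytic clearance are the secondary endpoints, and safety is primary. A patient who starts an interacting drug after consent could have altered exposure in one or both BMS-986177 periods. That patient would still count as compliant and would enter the by-dose PK and adverse event summaries unmarked.

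**Working it through.** The plan gives no figure on this point to reproduce, so the check is calendar arithmetic followed by an illustrative size.

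**Inputs**
- Consent-to-Day-1 lead L: up to 28 days (Protocol Table 2.-1 and Section 5.1). SAP Section 6.1 and Protocol Figure 5.1-1 still show 21, which is a separate mismatch. The lead can be as short as 1 to 3 days, because screening may be combined with Day -1 to -3.
- Dosing days d: 1, 5, 8 and 12. By the sequence table, BMS-986177 is given on Days 5 and 8 in sequences 1 and 4, and on Days 1 and 12 in sequences 2 and 3.
- Windows: 7 days for inhibitors and 28 days for inducers, both counted from consent.

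Days from consent to a dose = L + d − 1. For L = 28 this gives 28, 32, 35 and 39 days for the four dosing days. For L = 1 it gives 1, 5, 8 and 12.

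**Reading A: the window only looks back from consent.** Item 4 covers nothing after consent. Every listed drug is uncovered from consent to first dose. From first dose, Section 8.1 covers strong inhibitors and all inducers, which leaves moderate inhibitors open through Day 12.

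**Reading B: the window runs both ways from consent.** The inhibitor window has closed max(0, L + d − 1 − 7) days before each dose:

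| Lead L | Day 1 | Day 5 | Day 8 | Day 12 |
|---|---|---|---|---|
| 1 | 0 | 0 | 1 | 5 |
| 3 | 0 | 0 | 3 | 7 |
| 7 | 0 | 4 | 7 | 11 |
| 21 | 14 | 18 | 21 | 25 |
| 28 | 21 | 25 | 28 | 32 |

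Even at L = 1 the window has closed before Days 8 and 12, and every sequence has a BMS-986177 dose on one of those two days. The inducer window reaches Day 1 even at the longest lead (28 − 28 = 0), and Section 8.1 covers inducers afterwards.

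**Result by drug class**

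| Class | Before first dose, reading A | Before first dose, reading B | From first dose |
|---|---|---|---|
| Moderate inhibitors | uncovered | uncovered if L > 7 | not named in 8.1; uncovered throughout (A) or once the window has closed (B) |
| Strong inhibitors | uncovered | uncovered if L > 7 | covered by 8.1 |
| Inducers | uncovered | covered | covered by 8.1 |

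**Illustrative size.** Suppose an interaction multiplies AUC by r in k of the 24 planned completers (Protocol Section 5.2), all at the same dose. The geometric mean for that dose is then multiplied by r^(k/24). The documents give no r. Assuming r = 2:
- k = 1: 2^(1/24) = 1.029, a rise of 2.9%
- k = 2: 2^(2/24) = 1.059, a rise of 5.9%
- k = 3: 2^(3/24) = 1.091, a rise of 9.1%

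For r between 1 and 2 the shift lies between zero and these values. A larger r would exceed them.

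**The case against.** **An entry restriction and a stopping rule do different jobs.** A narrower class list for mandatory discontinuation may be deliberate and is not in itself a contradiction. That is fair. It does not explain why item 4 alone is tied to consent, and no other visible rule covers moderate inhibitors during treatment. Exclusion criterion 2b points to Section 7.7 as written, so it carries the gap with it. Investigator discretion under Section 8.1 is not a stated rule. Section 7.7.1 also permits maintenance medication without a CYP3A exception.

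**A reader might infer that inducers can also be taken during treatment, or that all the listed drugs are open for 28 days before dosing.** The documents do not support either. Section 8.1 names any inducer. Before first dose, inducers are uncovered only on reading A. For inhibitors, if item 4's own one-week length is used as a yardstick, only about the last 7 days before Day 1 matter. Users at the time of consent are caught on either reading, so only new starts and restarts escape.

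**A reader might infer that such use would go unseen.** It would not. Section 7.7.1 requires medications from 4 weeks before dosing and all concomitant therapies to be recorded, and SAP Section 7.4 summarizes concomitant medications by generic name and treatment. SAP Section 7.10.2 allows whole profiles to be excluded after review, with results shown both ways, and refers to a sponsor PK document that is not available here. What is missing from the visible plan is a pre-specified trigger: that exclusion is optional and does not mention interacting drugs.

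**A reader might infer a known bias in the 300 mg to 100 mg comparison.** No visible section plans that ratio. SAP Section 7.7 is descriptive by treatment, and Section 7.10.1 only sets decimal places for ratios. A drug continued through both BMS-986177 periods would move both geometric means and leave their ratio roughly unchanged. The visible text also does not say that BMS-986177 is a CYP3A substrate, although background sections are redacted. Restricting both inhibitors and inducers shows that the sponsor regards the interaction as relevant, but it gives no size.

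**Conclusion.** The point holds in a limited form. Item 4 of Section 7.7.1 uses a time anchor that differs from items 1 to 3, and Section 8.1 omits a drug class that item 4 restricts. On either reading of *within*, the stated rules leave moderate inhibitors uncovered around at least one BMS-986177 dose in every sequence. Strong inhibitors are uncovered only before first dose: on the look-back reading, or on the two-sided reading when consent is more than 7 days before Day 1. Inducers are uncovered only before first dose and only on the look-back reading.

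The effect on exposure cannot be quantified from the documents. The 2.9% to 9.1% range rests on an assumed doubling of AUC in one to three of 24 patients at the same dose. It would be smaller for weaker interactions or if affected patients were spread across doses. No effect on the safety endpoint is estimated. This is a modest issue in a descriptive study, worth correcting because it touches both the primary and secondary endpoints and the correction is cheap.

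**What to change.** **Protocol.** Reconcile the time anchor of Section 7.7.1 item 4 with items 1 to 3, state whether the window looks back only or runs both ways, and reconcile its drug classes with Section 8.1. The clinical team decides the windows and classes; no particular rule is proposed here.

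**SAP Sections 7.7 and 7.10.2.** Pre-specify that any BMS-986177 profile with recorded CYP3A inhibitor or inducer use inside the reconciled window is flagged in the listings, and that the PK parameter summary is repeated without flagged profiles. This would replace reliance on the discretionary exclusion for this purpose. The flagging rule should be fixed before concentrations are reviewed. The SAP change can be made on its own if dosing has finished.

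**Cost.** Protocol wording and one additional PK table. The medications are already recorded; flagging needs their start and stop dates, which should be confirmed on the CRF. The repeat summary would have slightly fewer profiles if any are flagged.

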7.7.2 Other Restrictions and Precautions

Not Applicable

7.8 Treatment After the End of the Study

At the end of the study, BMS will not continue to provide BMS supplied study treatment to participants/investigators unless BMS chooses to extend the study. The investigator should ensure that the participant receives appropriate standard of care to treat the condition under study.

Clinical Protocol
BMS-986177

CV010010
FXIa

8. DISCONTINUATION CRITERIA

8.1 Discontinuation from Study Treatment

Participants MUST discontinue investigational product (and non-investigational product at the discretion of the investigator) for any of the following reasons:

- Participant's request to stop study treatment. Participants who request to discontinue study treatment will remain in the study and must continue to be followed for protocol specified follow-up procedures. The only exception to this is when a participant specifically withdraws consent for any further contact with him/her or persons previously authorized by participant to provide this information
- Any clinical adverse event (AE), laboratory abnormality or intercurrent illness which, in the opinion of the investigator, indicates that continued participation in the study is not in the best interest of the participant
- Termination of the study by Bristol-Myers Squibb (BMS)
- Loss of ability to freely provide consent through imprisonment or involuntarily incarceration for treatment of either a psychiatric or physical (eg, infectious disease) illness
- Pregnancy
- Overt bleeding producing a Hb decrease ≥ 2 g/dL in 24 hours
- Need for blood transfusion
- Overt bleeding which is retroperitoneal, intracranial, intra-spinal, intraocular, or intraarticular
- Any overt bleeding deemed by the investigator to necessitate discontinuation of trial medication
- Medical or surgical treatment for bleeding beyond the application of pressure or cold compress
- Need for surgery during the study period
- Need for treatment with an anticoagulant or antiplatelet agent during the study period, with the exception of heparin and enoxaparin use during HD
- Need for treatment with a strong CYP3A4 inhibitor or any CYP3A4 inducers
- Inability to continue on the hemodialysis treatment for the duration of the study
- Inability to comply with the protocol
- Occurrence in one of the BMS-986177 treatment arm or in the enoxaparin treatment arm of 5 or more patients with events of complete clotting of HD circuit causing premature interruption of the HD procedure. This will result in a discontinuation of that treatment arm. The randomized sequence for the following patients will not be changed, and the discontinued treatment arm will be replaced by standard of care (UFH) in the treatment sequence.

In case a subject experiences complete clotting leading to premature interruption of HD in the BMS-986177 arms, the HD session can be restarted using standard of care at the discretion of the study Investigator.

Refer to the Schedule of Activities for data to be collected at the time of treatment discontinuation and follow-up and for any further evaluations that can be completed

Clinical Protocol
BMS-986177

CV010010
FXIa

All participants who discontinue study treatment should comply with protocol specified follow-up procedures as outlined in [Section 2](#). The only exception to this requirement is when a participant withdraws consent for all study procedures including post-treatment study follow-up or loses the ability to consent freely (i.e., is imprisoned or involuntarily incarcerated for the treatment of either a psychiatric or physical illness).

If study treatment is discontinued prior to the participant's completion of the study, the reason for the discontinuation must be documented in the participant's medical records and entered on the appropriate case report form (CRF) page.

8.1.1 Post Study Treatment Study Follow-up

Participants who discontinue study treatment may continue to be followed.

8.2 Discontinuation from the Study

Participants who request to discontinue study treatment will remain in the study and must continue to be followed for protocol specified follow-up procedures. The only exception to this is when a participant specifically withdraws consent for any further contact with him/her or persons previously authorized by participant to provide this information.

- Participants should notify the investigator of the decision to withdraw consent from future follow-up **in writing**, whenever possible.
- The withdrawal of consent should be explained in detail in the medical records by the investigator, as to whether the withdrawal is from further treatment with study treatment only or also from study procedures and/or post treatment study follow-up, and entered on the appropriate CRF page.
- In the event that vital status (whether the participant is alive or dead) is being measured, publicly available information should be used to determine vital status only as appropriately directed in accordance with local law.
- If the participant withdraws consent for disclosure of future information, the sponsor may retain and continue to use any data collected before such a withdrawal of consent.

